but still quite significant, 25% and 35% respectively.[8-11] Bone loss at the hip has been of lesser degree, and no bone loss was reported in the spine or the upper extremities of individuals with paraplegia. Correlation of bone loss with a number of demographic and clinical parameters has been evaluated with greatly varying results (review by Jiang[1]). To some extent, this is a function of the fact that the majority of the studies have involved small numbers of subjects, almost all have been cross-sectional and/or retrospective in nature, and many were not optimally controlled. However, it appears that in chronic SCI, bone mass is independent of age at time of injury, gender, and weight. Many studies have claimed a relationship between time since injury and BMD, suggesting that there is continued bone loss that occurs after the initial, acute period of rapid reduction in bone. This is an important point, as it would suggest that there is on-going bone resorption that exceeds bone formation and that a new “set-point” has not been reached. However, the majority of studies examining this point have been cross-sectional in nature, while the few longitudinal studies undertaken have not extended beyond 2-5 years, a period during which there may continue to be net bone loss.

Recently, Frotzler et al[3] have specifically examined this issue in detail, utilizing pQCT to determine changes in bone over a 30 month period (baseline, 15 months, 30 months) in 39 males with complete SCI and paralysis. Time of injury varied from 0.9 years to 39 years prior to study start. They report that BMD reached a new steady-state in the femur and the tibia within 3 to 8 years after onset of SCI, with the time scale depending on bone parameter and skeletal site, and that once the initial rapid phase of bone loss had occurred, bone status was stable and unrelated to time from injury (see Figure 1). In the few studies in which bone markers were examined in those with chronic SCI, levels were reported to be elevated many years after the acute injury, though markedly lower than in the immediate post-injury period.[12, 13]

[13] As with the majority of the studies evaluating BMD, these studies were also cross-sectional and not longitudinal in design.

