In man, treatment with antibody to sclerostin has been shown to result in significant increases in BMD in both post-menopausal women and men with OP. Specifically, romosozumab, a monoclonal antibody against sclerostin developed by Amgen, has not only shown increases in BMD but also reduction in fracture risk compared to both placebo and alendronate in randomized, controlled trials in post-menopausal women.[66, 67] In both trials, romosozumab was administered at a dose of 210 mg monthly for 12 months, followed by 12 months of either alendronate[67] or denosumab[66] treatment. Both BMD and fracture efficacy were evident after 12 months and maintained at 24 months. Compared to alendronate, both spine and hip BMD were greater at 12 months; and in a separate study, romosozumab treatment for 12 months resulted in greater increases in both spine and hip bone strength, determined by finite element modeling, than with teriparatide treatment.[68]

STUDY ENDPOINTS:

Primary Endpoint:

Change in integral vBMC at the knee (distal femur) at Month 12

Secondary Endpoints:

Change in DXA BMD at the total hip and femoral neck at Month 12

Change in vBMC at the hip at Month 12

Change in BMC/BMD at regions of interest around the knee at Month 12

Change in serum bone biomarkers at Month 12

Change will be assessed as both percent change from baseline and absolute change in all instances (see Statistical Analysis section below).

INVESTIGATIONAL AGENTS:

Romosozumab is a monoclonal antibody which inhibits sclerostin. It is marketed in the United States for the treatment of osteoporosis in post-menopausal women at high risk of fracture, defined as a history of osteoporotic fracture, or multiple risk factors for fracture; or who have failed or are intolerant to other available osteoporosis treatments. For this study, Amgen will provide romosozumab and a letter of cross-reference to their IND to satisfy CMC (Chemistry, Manufacturing, and Controls) and other documentation for FDA. Romosozumab will be stored in the locked and temperature-monitored refrigerator used solely for investigational drug products (IP) in our research space. The refrigerator is maintained in a locked room accessible only to research staff. All staff are required to sign in and sign out when opening the refrigerator, and a log is maintained of all activity. Dispensing of IP (both romosozumab and alendronate) is under the supervision of [name], PhD, principal investigator (PI) of this study.

STU00212405

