To reduce the number of people exposed, we have limited the sample size to 12. This should allow us to detect an effect size (ES) = 0.8 with 80% power and an alpha = 0.05 (or 90% power and an alpha = 0.10). This is based on using a Wilcoxon signed rank test (one sample) in G*power. If we increase the sample size to 15, we could detect an ES = 0.6 with 80% power and an alpha = 0.10. These ES estimates are based on changes in absolute BMD values (gm/cm²).

In order to study our primary and secondary endpoints, we will evaluate absolute changes from baseline to Month 12 for each using a non-parametric approach (primary analysis). An analysis evaluating percent changes from baseline to Month 12 will also be performed. The null hypothesis being tested for each outcome is the median difference between pairs of baseline and post-treatment values is zero. Assuming the expected sample size (12 subjects), we anticipate that the distribution of baseline and post-treatment scores across endpoints will not approximate a normal distribution. Given the dependency of the measures from each other, we will test the hypothesis that the average signed rank of the two samples is zero (Wilcoxon Signed Rank test) for each outcome for the primary analysis. The primary and secondary endpoints will also be assessed at Month 24 and compared to values at Month 12 and baseline.

STATEMENT OF COMPLIANCE

The study will be conducted in accordance with the International Conference on Harmonization guidelines for Good Clinical Practice (ICH E6) and the Code of Federal Regulations on the Protection of Human Participants (45 CFR Part 46). The Northwestern University IRB will review all appropriate study documentation to safeguard the rights, safety, and well-being of the subjects. All personnel involved in the conduct of this study will have completed human subject protection training. Informed consent will be obtained before any clinical trial-related procedures are conducted and will be on-going throughout the study.

DATA MANAGEMENT AND CONFIDENTIALITY

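### For the serum bone markers, the supplementary percent-change analysis should test the log ratio, because a signed-rank test on raw percent change favours rises over falls

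*Combined protocol and SAP*

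**What the plan says.** The Study Endpoints section lists "Change in serum bone biomarkers at Month 12" as a secondary endpoint and says that every endpoint is assessed on both the percent and the absolute scale. The Clinical chemistry evaluation subsection names two formation markers (P1NP and osteocalcin) and one resorption marker (CTX), with others to be decided.

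The Statistical Analysis and Sample Size Determination section says of the primary and secondary endpoints that "we will evaluate absolute changes from baseline to Month 12 for each using a non-parametric approach (primary analysis"). It then adds: "An analysis evaluating percent changes from baseline to Month 12 will also be performed". The null hypothesis is a median paired difference of zero, with no direction given. The Wilcoxon signed-rank test is tied in words to the primary analysis. No other test is named for percent change, and no log scale appears anywhere. Month 24 values are also to be compared with Month 12 and with baseline.

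The planning figures were set for bone mass, not for markers: "These ES estimates are based on changes in absolute BMD values (gm/cm²").

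**The concern.** The signed-rank test answers a question about the median only if the differences are symmetric about zero when there is no effect. The plan expects non-normal data but does not discuss symmetry.

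Suppose a woman is as likely to go from 50 to 100 as from 100 to 50. The absolute changes are +50 and −50, and the log ratios are +0.69 and −0.69; both pairs are symmetric. The percent changes are +100% and −50%, so the rise gets the larger rank. On the percent scale the test therefore leans towards finding a rise and away from finding a fall.

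That matters for this marker set. Objective 3 is the effect on serum bone markers, and the set mixes formation markers with a resorption marker, so changes in opposite directions would not be tested evenly. The Month 24 comparisons follow a year of alendronate, and the Background says that formation markers typically fall on anti-resorptive treatment. Falls are what a test on percent change detects least well.

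**Working it through.** **Inputs from the documents.** n = 12 ("we have limited the sample size to 12"); "effect size (ES) = 0.8 with 80% power and an alpha = 0.05"; "This is based on using a Wilcoxon signed rank test (one sample) in G*power". Sidedness is not stated. No SD, distribution or expected change is given for any marker.

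**The plan's own figure.** With a normal parent, the asymptotic relative efficiency method uses an effective N of 12 × 3/π = 11.46 and a noncentrality of 0.8 × √11.46 = 2.71. At alpha 0.05 this gives 81.1% power one-sided (simulation of the exact test 80.4%) and 69.0% two-sided (simulation 66.8%). The stated 80% is therefore reproduced as a one-sided figure. The missing statement of sidedness is a separate matter; both versions are given below.

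**Test used.** The exact two-sided 0.05 test at n = 12 rejects when W+ ≥ 65 or W+ ≤ 13. Each tail is 87/4096 = 2.12%. The exact one-sided test rejects at W+ ≥ 61, a level of 4.6%.

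**Assumed model.** Baseline = exp(m + e1) and follow-up = exp(m + d + e2), with each e normal with SD s. The assumed range is s = 0.15–0.40, and the SD of m (between women) is 0.3–0.8. The SD of the log ratio is s√2, so 0.15 × 1.414 = 0.21 and 0.40 × 1.414 = 0.57.

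**No effect (d = 0), two-sided 0.05, percent of trials:**

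| SD of log ratio | Percent change: rise / fall | Log ratio: rise / fall |
|---|---|---|
| 0.21 (s = 0.15) | 2.7 / 1.7 | 2.1 / 2.1 |
| 0.30 | 3.0 / 1.6 | 2.1 / 2.1 |
| 0.50 | 3.8 / 1.3 | 2.1 / 2.1 |
| 0.57 (s = 0.40) | 4.0 / 1.2 | 2.1 / 2.1 |

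The totals for percent change run from 2.7 + 1.7 = 4.4% to 4.0 + 1.2 = 5.2%. The total error is sound; its split is not. With a one-sided test, a rise is called in 5.9–8.8% and a fall in 3.6–2.6%, against 4.6%.

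**Power for a fall of 0.8 SD of the log change.** The shift is 0.8 × 0.21 = 0.17 (a 16% fall) at s = 0.15 and 0.8 × 0.57 = 0.45 (a 36% fall) at s = 0.40.

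| Scale | Two-sided 0.05 | One-sided 0.05 |
|---|---|---|
| Percent change, s = 0.15 to 0.40 | 61% to 51% | 75% to 66% |
| Log ratio | 67% | 80% |

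**Equal-fold changes.** With an SD of the log ratio of 0.5 and a two-sided test, percent change detects a 1.5-fold rise with 77% power and a fall to 1/1.5 with 54%. The log ratio gives 68% for both.

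**Absolute change.** When baseline and follow-up are exchangeable under no effect, each tail is 2.0–2.2%. Two-sided power for the same 0.8 SD fall is 65–60% under the multiplicative model above, 2 to 7 points below the log ratio. Under an additive model (assumed error SD 0.1 of the median level, constant absolute shift of 0.8 SD of the change) the order reverses. Absolute change has 67%, against 65%, 62.5% and 59% for the log ratio at between-woman log SDs of 0.3, 0.5 and 0.8.

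**Bone mass.** At an assumed SD of the log ratio of 0.05, percent change and log ratio differ by about 1 point.

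**The case against.** The strongest reply is that the signed-rank test is assigned explicitly only to absolute change, so the defect sits in an analysis for which no test is named. That stands as a limit on the wording. It does not remove the point, because no other test is offered and a reader would apply the same one.

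A second reply is that the size is borrowed. Lognormal markers and their SDs are assumptions, and the 0.8 SD effect comes from BMD. This also stands. At the low end of the range the lean is small. With large effects it hardly matters: for an assumed fall to 60% of baseline (log SD 0.2 per sample, 0.5 between women), all three scales have at least 99.8% two-sided power. The direction of the lean, however, is arithmetic and does not depend on the SD.

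A reader might go further and infer that absolute change should also give way to the log ratio as the primary marker scale, at no cost. The documents do not support that. The loss under multiplicative variation becomes a gain of about 2 to 8 points under additive variation, and nothing in the plan says which holds. The Background remark that in chronic injury "levels were reported to be elevated many years after the acute injury, though markedly lower than in the immediate post-injury period" does not settle it. Entry requires at least 6 months since injury, and the remark does not say how far baselines differ among eligible women. One caveat remains: if the fold change is independent of baseline, absolute change also leans upwards (upper tail 2.6–4.7%). Its validity therefore rests on exchangeability.

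**Conclusion.** The point holds for the supplementary percent-change analysis of the serum markers. If that analysis uses the signed-rank test, its error is split unevenly (2.7–4.0% for rises, 1.7–1.2% for falls, two-sided 0.05). It also gives up about 6 to 16 points of power for a fall (67 − 61 to 67 − 51). The log ratio removes the lean under both multiplicative and additive error, because it is symmetric whenever the two values are exchangeable.

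The sizes rest on an assumed within-woman log SD of 0.15–0.40 and on a 0.8 SD shift. Confidence is high in the direction and moderate in the amount. It would be wrong to infer that overall type I error is inflated in any important way, that the primary CT endpoint is affected, or that the planned primary scale is invalid. This is a modest, nearly free improvement to a supplementary analysis of a secondary endpoint.

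**What to change.** Add one sentence to the statistical section. For P1NP, osteocalcin, CTX and any further serum marker, the relative-change analysis is a Wilcoxon signed-rank test on log(follow-up) minus log(baseline), with the back-transformed ratio reported as the percent change. Apply the same rule to Month 24 against baseline and, with Month 12 as the reference, to Month 24 against Month 12. Do not run a signed-rank test on raw percent change for the markers. Name the test for percent change in the remaining endpoints, where the choice of scale makes almost no difference.

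Keep absolute change as the primary scale. The change needs no new data or samples and keeps a percent figure for readers. Because the samples are assayed at the end of the trial, the scale can be fixed before any marker result exists.

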APPENDIX A**Study Procedures Flowsheet**

Event	Screening	Baseline	Study Visits															
			0	Mo 1	Mo 2	Mo 3	Mo 4	Mo 5	Mo 6	Mo 7	Mo 8	Mo 9	Mo 10	Mo 11	Mo 12	Mo 15	Mo 18	Mo 24
Study Day	V1	V2	V3	V4	V5	V6	V7	V8	V9	V10	V11	V12	V13	V14	V15*	V16	V17	
Procedures:																		
Informed Consent	X																	
Demographic Data	X																	
Concomitant Medication	X	X	X	X	X	X	X	X	X	X	X	X	X	X	X	X	X	
Height	X																	
Weight	X																	
Vital Signs	X	X	X	X	X	X	X	X	X	X	X	X	X	X	X	X	X	
Medical History	X																	
Physical Exam	X																	
EKG	X																	
Urine pregnancy test	X	X	X	X	X	X	X	X	X	X	X	X	X	X	X	X	X	
Adverse Event Assessment		X	X	X	X	X	X	X	X	X	X	X	X	X	X	X	X	
Confirm Patient Meets Incl/Excl Criteria	X	X																
Administer/Dispense Study Drug	X	X	X	X	X	X	X	X	X	X	X	X	X	X	X	X	X	
Dispense Calcium/Vitamin D	X															X	X	X
Assess Compliance with calcium/vit D			X		X		X		X		X		X		X	X	X	X
WISCI	X	X														X		X
DXA Lumbar Spine (A-P View)	X															X		X
DXA Hip ROIs	X															X		X
CT Distal Femur/Proximal Tibia	X															X		X
CT Hip	X															X		X
Labs:																		
CBC	X															X		
Chemistry Panel/Serum Calcium	X		X													X		
FSH and Estradiol	X																	
TSH	X																	
25(OH) Vitamin D	X		X													X		
iPTH (I-84)	X																	
Urinalysis	X																	
Bone Markers		X			X				X			X			X		X	

*may be replaced with telephone call

**Serum Calcium and Vitamin D will be repeated at Mo 3 only if Mo 1 labs are abnormal.
